2.3.2 Inclusion Criteria

Women who meet the following criteria will be eligible for the study:

- 1) Postpartum women
- 2) No antenatal diagnosis of hypertensive disorder of pregnancy at the time of admission for delivery, defined as existing chronic hypertension diagnosis or documented blood pressure of ≥ 140 systolic OR ≥ 90 diastolic on at least 2 occasions at least 4 hours apart

prior to delivery admission who do not go on to get magnesium for seizure prophylaxis by the time of delivery

- 3) At least 18 years of age
- 4) English or Spanish speakers
- 5) One or more of the following high risk factors and/or two or more moderate risk factors for development of de novo postpartum hypertension:
 - a. High risk
 - i. Pregestational diabetes mellitus
 - ii. Renal disease
 - iii. Autoimmune disease (systemic lupus erythematosus, antiphospholipid syndrome)
 - iv. Multifetal gestation
 - v. Gestational diabetes mellitus, A2 (i.e. medication-dependent)
 - vi. History of preeclampsia in a prior pregnancy (not including the index pregnancy)
 - b. Moderate risk
 - i. Primiparity
 - ii. Obesity (BMI $\geq 35 \text{ kg/m}^2$)
 - iii. Age ≥ 35 years
 - iv. Black or African-American race
 - v. Family history of preeclampsia

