Specific Aim 2. To compare rates of initiation of hypertensive therapies in women randomized to the study drug compared to those randomized to placebo. We hypothesize that women randomized to the study drug will be less likely to be initiated on hypertensive therapies between delivery and 6 weeks postpartum.

Specific Aim 3. To compare rates of severe maternal morbidity in women randomized to the study drug compared to those randomized to placebo from the time of discharge to 6 weeks postpartum. We hypothesize that women randomized to the study drug will have lower rates of severe maternal morbidity between delivery and 6 weeks postpartum compared to those randomized to placebo.

- **Sub-aim 1: To compare hypertensive-related unscheduled presentations between those who have been randomized to the study drug and those randomized to placebo.** We hypothesize that women randomized to the study drug will have fewer triage and emergency department visits for hypertension-related complaints episodes after discharge.
- **Sub-aim 2: To assess adverse effects of therapy in the study group and the control group.** We hypothesize that there will be no difference in adverse effects, such as discontinuation of breastfeeding, hypotension, and electrolyte abnormalities in women randomized to the study drug compared to those randomized to placebo.
- **Sub-aim 3: To analyze factors associated with incidence of severe maternal morbidity in the study group and the control group.** We hypothesize that factors such as racial and ethnic identity and age will be associated with increased incidence of severe maternal morbidity.

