2.3 Methods

2.3.1 Study Design

This will be a randomized control trial, in which women who are at high risk of developing de novo postpartum hypertension will be assigned to either a five-day course of PO furosemide 20 mg daily or a five-day course of PO placebo after delivery.

Patients will be informed of the study in the antenatal period, within four weeks of their estimated date of delivery or on admission to labor and delivery and will be deemed eligible, enrolled and randomized from the postpartum service within 8 hours after delivery.

Randomization will be performed by the Columbia Research Pharmacy, and the study drug or placebo will be dispensed to the postpartum floor to be administered by the patient's assigned postpartum nurse. Blood pressure measurements will occur every six hours (or more if clinically indicated) until the time of discharge. Upon discharge, the remainder of the five-day course of the study drug or placebo will be dispensed to the patient to complete. Patients in both groups will be asked to check their blood pressure twice per day, once in the morning and once in the evening, and will receive text message reminders twice a week. In order to check their blood pressures after discharge, patients in both groups will be given a Philips Bluetooth-enabled blood pressure cuff, which will transmit blood pressure measurements via Bluetooth from the monitor to the eCC. These patients will be educated on the use of and enrolled in the software by research investigators who have been in-serviced on the devices prior to discharge. The tablets are cellular-enabled, so no wireless connection is needed in the patient's home. Criteria for contacting their provider will be reviewed with and provided in writing to the patients upon discharged. No changes will be made to standard hypertensive treatment protocols for either group.

Patients in both groups will be given an appointment to follow-up with their obstetric provider in the office at approximately 14 days postpartum and at about 6 weeks postpartum. The number of measurements *total* and the number of measurements that were *elevated* will be ascertained for each group at this visit.

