2.3.4 Recruitment, Screening and Enrollment

Recruitment and Screening

A study team member will perform daily chart screen of all women at least 36 weeks of gestation who are presenting for prenatal visit with a CUIMC provider and of all women admitted to the CUIMC labor and delivery unit (CHONY 10 Tower) for delivery. Permission from healthcare providers will be obtained prior to the OB study team member contacting participants. Women will be approached at the aforementioned times to be informed of the study and of their conditional eligibility. Final eligibility will be determined on admission to labor and delivery and eligible women will then be recruited on the postpartum units (CHONY 5 central, 6 central and 10 central).

We will abide by the CUMC policy that researchers cannot directly approach a patient for recruitment until that patient has been informed of the study by a provider who has ascertained that the patient is willing to discuss the study with the investigators. This will be documented in the research record.

We will also ensure that if patients are laboring, they are competent to consent to research and haven't received systemic opioids or sedative medications within the past 2 hours. We will also ensure the cooperation of the labor room nurse, obstetric care provider, and patient support persons in the discussion of proposed research and study informed consent process. Whenever practical and feasible, information about research on Labor and Delivery will be made available to patients prior to onset of painful labor and/or after placement of epidural analgesia, if such analgesia is desired by the patient.

Informed Consent Process

Research coordinators and study physicians listed on this protocol may obtain informed consent. Study personnel will consent participants in person, face-to-face, when they receive notification by a provider of an eligible patient. Participants will be consented in English or Spanish by personnel fluent in that language or with the use of NYP translators and a full consent in their language. Recruitment will occur in a private setting, in a non-coercive manner, with ample time to ask questions and receive satisfactory answers.

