2.3.8 Definitions

Chronic hypertension will be defined according to ACOG guidelines as blood pressure measurement of EITHER ≥ 140 mm Hg OR diastolic ≥ 90 mm Hg on at least 2 occasions, at least 4 hours apart, prior to 20 weeks gestation.²

Hypertensive disorders of pregnancy will be defined according to ACOG guidelines.² The minimum criteria for a diagnosis of HDP are as follows:

- Blood pressure measurement of EITHER systolic ≥ 140 mm Hg OR diastolic ≥ 90 mm Hg on at least 2 occasions, at least 4 hours apart, between 20 weeks gestation and delivery
- Blood pressure measurement of EITHER systolic ≥ 160 mm Hg OR diastolic ≥ 110 mm Hg on at least 2 occasions qualifies as severe features

Diagnosis of hypertensive disorder of pregnancy will be determined at the time of admission for delivery.

The following investigations are routinely undertaken in the clinical setting once HDP is identified in order to further categorize HDP into more specific diagnoses. These results will be reviewed for each patient to ensure the correct diagnosis has been assigned to the patient. Blood pressure findings as above with none of the findings listed in the table below satisfies a diagnosis of gestational hypertension.

Type of test	Cutoffs	Diagnosis
--------------	---------	-----------

Urine	
 -24-hour protein concentration > 300 mg OR -Protein/Creatinine ratio > 0.3 	Preeclampsia
Serum	
 -Platelets $<100,000/\text{microliter}$ OR -Creatinine $>1.1 \text{ mg/dL}$, or doubling from baseline OR -LFTs $>$ twice the upper limit of normal concentration or twice baseline 	Preeclampsia with severe features
Signs/symptoms: any of the following, if not accounted for by another diagnosis	
 -New-onset, refractory cerebral or visual disturbances -Severe persistent right upper quadrant or epigastric pain unresponsive to medication -Pulmonary edema -Blood pressure ≥ 160 systolic OR ≥ 110 diastolic 	Preeclampsia with severe features
Serum	
 -Platelets $<100,000/\text{microliter}$ AND -Evidence of hemolysis AND -LFTs $>$ twice the upper limit of normal concentration or twice baseline 	Hemolysis, elevated liver enzymes and low platelet count (HELLP) syndrome
Signs/symptoms	New-onset, grand mal seizure, with no history of seizure disorder and not accounted for by any other diagnosis	Eclampsia

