De novo postpartum hypertensive disorders of pregnancy will be defined according to the aforementioned criteria and definitions, except for their timing of occurrence after delivery, and in the absence of any antenatal diagnosis of a hypertensive disorder of pregnancy.

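### Eligibility says nothing about the hours between delivery and randomisation, yet events are counted from delivery, so some counted events may precede any study drug

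*Combined protocol and SAP*

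**What the plan says.** **Eligibility.** Inclusion item 2 (2.3.2) requires "No antenatal diagnosis of hypertensive disorder of pregnancy at the time of admission for delivery". Its blood pressure limb stops at admission, and its only later element is magnesium: "prior to delivery admission who do not go on to get magnesium for seizure prophylaxis by the time of delivery". Section 2.3.8 agrees on timing: "Diagnosis of hypertensive disorder of pregnancy will be determined at the time of admission for delivery". The three exclusions in 2.3.3 concern language, a contraindication to diuretics, and diuretic use before delivery.

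**When eligibility is settled.** Section 2.3.4 says "Final eligibility will be determined on admission to labor and delivery", while 2.3.1 says that women "will be deemed eligible, enrolled and randomized from the postpartum service within 8 hours after delivery". The consent text in 2.3.4 adds that women who still satisfy the inclusion criteria are randomised within eight hours of delivery. The first dose has the same eight-hour limit.

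**When counting starts.** Sub-aims 1 and 2 of Aim 1 (2.2) run from delivery to 6 weeks. The Aim 2 hypothesis is that women on the study drug will be "less likely to be initiated on hypertensive therapies between delivery and 6 weeks postpartum". Section 2.3.6 gives secondary outcomes 1, 2, 3 and 5 assessment times but no start.

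**What counts as a case.** Section 2.3.8 applies the antenatal criteria to de novo disease "except for their timing of occurrence after delivery, and in the absence of any antenatal diagnosis of a hypertensive disorder of pregnancy".

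**The concern.** The stated purpose (2.1) is to find out whether furosemide can help prevent de novo postpartum hypertension. An event that has already occurred when a woman is randomised cannot be prevented. Followed as written, the plan admits such women and puts their events in the numerator of both arms. The observed contrast then mixes events that the drug might influence with events that it cannot, and a true benefit looks smaller than it is. Women who were hypertensive in labour but not given magnesium also pass inclusion item 2, because its blood pressure test ends at admission. If their raised readings continue after delivery, they can be recorded as de novo cases.

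**Working it through.** **Step 1. Can an event precede randomisation and still count?**

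| Question | Text | Answer |
|---|---|---|
| Last time blood pressure is tested for eligibility | 2.3.2 item 2; 2.3.8 | Admission for delivery |
| Last time magnesium is tested | 2.3.2 item 2 | Delivery |
| Exclusion for hypertension, magnesium or an antihypertensive after delivery | 2.3.3 | None |
| Latest randomisation and first dose | 2.3.1; 2.3.4 | 8 hours after delivery |
| Start of counting | 2.2, Sub-aims 1 and 2, Aim 2 hypothesis | Delivery |

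The case definition needs two readings at least 4 hours apart. Readings at 1 and 6 hours after delivery are 5 hours apart and both fall within the 8 hours. The ward schedule is six-hourly, or more often if clinically indicated (2.3.1), so such a pair is possible. Starting magnesium or an antihypertensive needs no second reading. Checking again that a woman still meets the inclusion criteria does not remove her, because those criteria contain nothing after delivery.

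**Step 2. How much dilution?** The plan gives no figure to reproduce here: it states no expected event rates and no frequency of onset in the first hours. Its sample size of 41 per group is for mean arterial pressure (2.4.1) and is not in question. All three inputs below are therefore assumptions:

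- q, the share of women in each arm with the event before randomisation: 5% or 10%, which is about 2 or 4 of 41
- later event rate r among the remaining women on placebo: 20%
- later event rate r among the remaining women on drug: 10%

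Counted rate = q + (1 − q) × r.

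- q = 0: 0.20 and 0.10. Risk ratio 0.50, difference 10.0 points.
- q = 0.05: placebo 0.05 + 0.95 × 0.20 = 0.240; drug 0.05 + 0.95 × 0.10 = 0.145. Risk ratio 0.145/0.240 = 0.60, difference 9.5 points.
- q = 0.10: placebo 0.10 + 0.90 × 0.20 = 0.280; drug 0.10 + 0.90 × 0.10 = 0.190. Risk ratio 0.190/0.280 = 0.68, difference 9.0 points.

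**Step 3. Are these values of q plausible?** They imply that 0.05/0.24 = 21% or 0.10/0.28 = 36% of all placebo-arm events over six weeks fall before randomisation. Nothing in the documents supports or rules out shares of that size. They are better read as an illustration than as an expectation.

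**Step 4. What does this do to a test on 41 per arm?** The exact power of the uncorrected chi-squared test at two-sided 5% is about 25% with q = 0, 20% with q = 0.05 and 16% with q = 0.10.

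**The case against.** The strongest reply is that the harm is small and has no direction. Events before randomisation cannot depend on allocation, so they balance on average. The absolute difference barely moves. The outcomes concerned are secondary, and on the assumed rates they have only about 25% power even with no early events. Eight hours is a maximum, and the lay abstract (1.2) places onset at two days to six weeks, although the scientific abstract (1.1) says immediate to late. Section 2.3.4 also describes women as enrolled from randomisation, which could be read as the intended start of counting. All of this stands as a limit on weight. It does not close the gap: the aims in 2.2 say delivery, and no text screens for what happens after it.

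A reader might go further and infer one of three things that the documents do not support:

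- **That the comparison is biased towards one arm.** Randomisation comes after these events, so the expectation is dilution only.
- **That the plan means to enrol women who are already hypertensive.** It is silent on them. Staff may well screen them out, but no written rule says so.
- **That the primary analysis is materially weakened.** The mean arterial pressure window in 2.3.6 ends at antihypertensive initiation if that comes before discharge. For a woman treated very early it could lie wholly or mostly before study drug. That follows from the wording, but the documents do not say how many women this would affect, so no loss of power can be attributed to it.

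**Conclusion.** The concern holds as a mismatch between eligibility, time of randomisation and start of counting. Blood pressure is judged to admission, magnesium to delivery, and nothing from then to randomisation, while the aims count events from delivery. Events that the drug could not have prevented can therefore be counted. The expected consequence is attenuation, balanced on average between arms. On assumed later rates of 20% and 10%, with 5 to 10% prior events, the risk ratio moves from 0.50 to 0.60 to 0.68 and the absolute difference from 10 to 9.5 to 9.0 points. These figures rest wholly on assumed inputs, and the true size may be much smaller. The stated sample size needs no change. The case for acting is that the window as written does not match a prevention question and that the correction is cheap. It does not rest on a demonstrated large effect.

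**What to change.** 1. **Event window.** In 2.2, start Sub-aims 1 and 2 of Aim 1 and Aim 2 at randomisation. In 2.3.6, state the same start for secondary outcomes 1, 2, 3 and 5. Report events between delivery and randomisation separately, by arm. Randomisation is a cleaner start than first dose because it keeps the comparison as allocated.
2. **Status at randomisation.** Add to 2.3.3 that a woman is not randomised if, between delivery admission and randomisation, she already meets the protocol's own hypertensive-disorder definition or has already had an outcome treatment (magnesium for seizure prophylaxis or an antihypertensive). Starting at admission also covers hypertension in labour. If the investigators prefer to keep such women, record this status at randomisation and leave them out of the at-risk set for those event outcomes. Because the status is fixed before allocation, that set remains a randomised comparison.
3. **Timing of eligibility.** Reconcile 2.3.1 with the recruitment and consent text in 2.3.4, so that eligibility is conditional at admission and final at randomisation.

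The cost is one chart check at the existing randomisation step, some wording, and a few screened women lost. Section 2.4.3 describes a large eligible cohort, so recruitment should bear this easily.

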2.3.3 Exclusion Criteria

- 1) Non-English and Non-Spanish speakers
 - The consent form will only be available in these 2 languages
- 2) Women with a contraindication to diuretic therapy
- 3) Women who have used diuretics in the two weeks prior to delivery

2.3.4 Recruitment, Screening and Enrollment

Recruitment and Screening

A study team member will perform daily chart screen of all women at least 36 weeks of gestation who are presenting for prenatal visit with a CUIMC provider and of all women admitted to the CUIMC labor and delivery unit (CHONY 10 Tower) for delivery. Permission from healthcare providers will be obtained prior to the OB study team member contacting participants. Women will be approached at the aforementioned times to be informed of the study and of their conditional eligibility. Final eligibility will be determined on admission to labor and delivery and eligible women will then be recruited on the postpartum units (CHONY 5 central, 6 central and 10 central).

We will abide by the CUMC policy that researchers cannot directly approach a patient for recruitment until that patient has been informed of the study by a provider who has ascertained that the patient is willing to discuss the study with the investigators. This will be documented in the research record.

We will also ensure that if patients are laboring, they are competent to consent to research and haven't received systemic opioids or sedative medications within the past 2 hours. We will also ensure the cooperation of the labor room nurse, obstetric care provider, and patient support persons in the discussion of proposed research and study informed consent process. Whenever practical and feasible, information about research on Labor and Delivery will be made available to patients prior to onset of painful labor and/or after placement of epidural analgesia, if such analgesia is desired by the patient.

Informed Consent Process

Research coordinators and study physicians listed on this protocol may obtain informed consent. Study personnel will consent participants in person, face-to-face, when they receive notification by a provider of an eligible patient. Participants will be consented in English or Spanish by personnel fluent in that language or with the use of NYP translators and a full consent in their language. Recruitment will occur in a private setting, in a non-coercive manner, with ample time to ask questions and receive satisfactory answers.

Patient written informed consent and HIPAA authorization to participate in the study will be collected on an iPad or laptop. In-person electronic signature will be captured on the electronic informed consent form. Study personnel obtaining consent will be physically present at time of signature. A paper copy of the signed informed consent form will be given to the patient. A copy of the signed consent form will also be placed in the patient's inpatient paper chart. The time of consent will be documented on the consent form and in the medical record.

Consent forms will be available in both English and Spanish to accommodate our expected population. A witness will be required for our non-English speaking patients.

At the time of the consent, the Informed Consent Process will begin with a concise and focused presentation of the key information about the research study. The collaborating investigators will explain the study, and potential subjects will have an opportunity to discuss the information provided. The collaborating investigators will answer any questions. The Informed Consent Process as a whole presents information in sufficient detail relating to the research study. Consent will be obtained to measure blood pressures postpartum. Consent will be obtained to review medical records to abstract pertinent sociodemographic and clinical information and to call patients to obtain the aforementioned information if not able to be abstracted from the medical record. Consent will be obtained to administer electronic surveys and collect home blood pressure measurements at two postpartum study visits. Patients still meeting inclusion criteria will be randomized at within eight hours of delivery on the postpartum service.

Enrollment

After obtaining written informed consent, participants will be randomized to either the study drug, as defined above, or placebo. Randomization will occur through the Columbia Research Pharmacy in REDCap. The medication intervention will be dispensed to the patient's postpartum unit and administered by the nursing staff once daily beginning within eight hours of delivery. The patient, the patient's nurse, and the patient's inpatient obstetric provider will not be informed

of the patient's randomization group, to avoid potential biases stemming from differences in inpatient care. Participants will be enrolled in the study from the time of randomization until 6 weeks postpartum.

2.3.5 Equipment and Software

All study participants will receive a Philips Home Telehealth Solution kit, complimentary of participating in the study, which includes several FDA/FCC approved devices. NewYork-Presbyterian has a contract in place with Philips (attached separately to this IRB application under "Philips Contract 5.10.21") which allows the hospital to utilize Philips telehealth programs for its patients. **The investigators had no role in the signing of this contract and have no financial interests in this program.** The following equipment is included in the Philips kit:

Device	US 510(k)
A&D Blood Pressure Meter, regular or small cuff version UA-767PBT-Ci	Class II K043217 FCC:POOWML-C40
eCareCoordinator (eCC) Suite	K171029
Samsung Galaxy Tab E 8.0" model SM-T377A	Not a medical device, no associated 510(k) FCC: A3LSMT377A

The instructions that patients will receive for use of the tablet and the blood pressure meter are attached separately to this IRB application ("Philips A&D Cuff Instructions").

At the conclusion of the 6-week study period (in other words, after the scheduled postpartum visit or the time when that visit was supposed to occur, if the patient did not present), the patient will be expected to return the kit. The full patient terms of use are attached to this IRB application as a separate document ("Philips Patient Terms of Use").

